3.1 STUDY OUTCOME MEASURES

The study will end after 36 months or at the point where the predetermined number of participants have been recruited; and 24-month follow up phone call has been completed for those with DUO-EF suggestive of LVEF<40% but gold-standard LVEF >40%.

Primary outcome measure:

- **Sensitivity, specificity for DUO-EF detecting LVEF above or below 40%**

Secondary outcome measures:

- DUO-EF performance against subgroup %LVEF calculated by cardiac MRI
- Consistency of DUO-EF result at point-of-care in GP practice ('real world' use where GP suspects new heart failure) against repeat DUO-EF at time of gold-standard investigation; similarly with patients attending Covid-19 follow up clinic with symptoms of LVEF <40%
- Development of LVEF <40% at 24 months in participants with initial DUO-EF suggestive of LVEF <40% but gold standard investigations LVEF >40% i.e. can DUO-EF predict future development of LVEF <40%
- DUO-EF point-of-care determination of LVEF<40% in comparison with the components of the established NICE pathway (BNP result)

4. PARTICIPANT ENTRY

4.1 PRE-REGISTRATION EVALUATIONS

No pre-registration screening or tests are required.

4.2 INCLUSION CRITERIA & EXCLUSION CRITERIA

Inclusion criteria for all	
 - Age 18 years or above - Able to give informed consent 		
	Group 1	Group 2	Group 3
Additional inclusion criteria	
 - Patient attending for departmental echo or cardiac MRI 	
 - GP concerned about heart failure diagnosis and initiates patient onto routine NICE pathway 	
 - Attending COVID-19 follow-up clinic and clinician concerned about heart failure diagnosis and initiates patient onto routine NICE pathway
Exclusion criteria	
 - Any chest wound, skin pathology or other feature that would prohibit routine stethoscope examination 		

4.4 WITHDRAWAL CRITERIA

Participants are free to withdraw their consent from the study at any point.

5. ADVERSE EVENTS AND RISK

False negative & False Positive Results

This study poses minimal to no risk to participants. The Eko DUO device's capability to record ECG is fully CE marked and is already in mainstream clinical use. There are no 'side-effects' or contact hazards. There is a risk of a 'false negative' DUO-EF reading in those who in fact do have LVEF <40; however this is already accounted for in this study since DUO-EF is not interfering with the standard of care (e.g. echocardiography to definitively determine LVEF).

5.1 DEFINITIONS

Adverse Event (AE): any untoward medical occurrence in a patient or clinical study subject.

Serious Adverse Event (SAE): any untoward and unexpected medical occurrence or effect that:

- **Results in death**
- **Is life-threatening** – refers to an event in which the subject was at risk of death at the time of the event; it does not refer to an event which hypothetically might have caused death if it were more severe
- **Requires hospitalisation, or prolongation of existing inpatients' hospitalisation**
- **Results in persistent or significant disability or incapacity**
- **Is a congenital anomaly or birth defect**

Medical judgement should be exercised in deciding whether an AE is serious in other situations. Important AEs that are not immediately life-threatening or do not result in death or hospitalisation but may jeopardise the subject or may require intervention to prevent one of the other outcomes listed in the definition above, should also be considered serious.

5.3 REPORTING PROCEDURES

All adverse events should be reported. Depending on the nature of the event the reporting procedures below should be followed. Any questions concerning adverse event reporting should be directed to the Chief Investigator in the first instance.

5.3.1 Non serious AEs

All such events, whether expected or not, should be recorded.

5.3.2 Serious AEs

An SAE form should be completed and faxed to the Chief Investigator within 24 hours. However, relapse and death, and hospitalisations for elective treatment of a pre-existing condition do not need reporting as SAEs.

All SAEs should be reported to the <name of REC> where in the opinion of the Chief Investigator, the event was:

- 'related', ie resulted from the administration of any of the research procedures; and
- 'unexpected', ie an event that is not listed in the protocol as an expected occurrence

Reports of related and unexpected SAEs should be submitted within 15 days of the Chief Investigator becoming aware of the event, using the NRES SAE form for non-IMP studies. The Chief Investigator must also notify the Sponsor of all SAEs.

Local investigators should report any SAEs as required by their Local Research Ethics Committee, Sponsor and/or Research & Development Office.

Contact details for reporting SAEs
[contact]
CI email (and contact details below)
Fax: **xxx**, attention **xxx**
Please send SAE forms to: **xxx**
Tel: **xxx** (Mon to Fri 09.00 – 17.00)

6. ASSESSMENT AND FOLLOW-UP

Please see table below describing follow up procedures for different groups of the study. Describe how incidental findings will be identified, reviewed and reported, and to which individuals they will be reported to (i.e. GP, clinical care team).

	Group 1: All-comers to echo/cardiac MRI	Group 2: GP patients	Group 3: COVID-19 follow-up clinic
Follow-up	Follow-up phone call at 24 months for all patients with positive DUO-EF but negative gold standard investigations for LVEF <40% (to evaluate if positive DUO-EF is an indicator of future risk for developing LVEF <40%)		

The recruitment for the study will end when the requisite number of participants has been achieved. For some groups, there will be a long-term follow up period as described above. The study will end upon completion of these follow up periods.

In those patients where a 24 month follow up phone call is indicated, we will first attempt to confirm whether or not the participant is deceased by review of the NHS Spine, thereby avoiding unnecessary distress for relatives.

Incidental Findings

Incidental findings are highly unlikely in the course of this study since the process of having DUO-EF would not identify anything additional to what would be found during standard of care. In the unlikely event of the study team making an incidental finding they will notify the team in charge of the patient's care at the time-of-appointment.

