cMRI	cardiac magnetic resonance imaging

KEYWORDS

- COVID-19
- Heart failure
- Ejection fraction
- Machine learning

STUDY SUMMARY

TITLE DUO-EF-19: Diagnosis of Heart Failure in the Post-COVID-19 Clinic, Primary Care and Hospital Setting Using a Digital Stethoscope with AI ECG

DESIGN Prospective cross-sectional study

AIMS

1. To validate detection of left ventricular ejection fraction (LVEF) above or below 40% using single-lead ECG interpreted by machine learning algorithm (DUO-EF) compared to gold-standard investigations for calculating LVEF (echocardiography [echo], and a subgroup in cardiac MRI [cMRI])
2. To conduct a real-world evaluation of DUO-EF detection of LVEF above or below 40% in the primary care and COVID-19 follow up clinic setting; validated against subsequent gold standard investigations
3. To evaluate the positive and negative-predictive value of DUO-EF at 24 months

Methods

1. Head-to-head comparison of DUO-EF against gold standard investigation (echo and cMRI) for classifying LVEF<40%; in unselected patients attending for routine echocardiography (main study group) and cardiac MRI (subgroup) as part of their routine clinical care
2. Point-of-care DUO-EF in patients where GP suspects new heart failure and comparison with:
 - a. Subsequent DUO-EF at time of gold-standard investigation (if indicated as standard of care)
 - b. Ejection fraction as calculated by gold-standard investigation
3. Point-of-care DUO-EF in patients attending COVID-19 follow up clinic where clinician suspects new heart failure and comparison with:
 - a. Subsequent DUO-EF at time of gold-standard investigation for HF
 - b. Ejection fraction as calculated by gold-standard investigation

Telephone call follow-up at 24 months for all patients with DUO-EF suggestive of HFrEF but normal gold standard investigations

**OUTCOME
MEASURES**

- **1.) Primary: Sensitivity and specificity of DUO-EF for detecting LVEF above or below 40%**
- 2.) Secondary:
 - DUO-EF performance against subgroup LVEF calculated by cardiac MRI
 - Consistency of DUO-EF result at point-of-care in GP practice ('real world' use where GP suspects new heart failure) against repeat DUO-EF at time of gold-standard investigation
 - Consistency of DUO-EF result at point-of-care in Covid-19 follow up clinic ('real world' use where clinician suspects new heart failure) against repeat DUO-EF at time of gold-standard investigation

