 - Development of LVEF <40% at 24 months in participants with initial DUO-EF suggestive of LVEF <40% but gold standard investigations LVEF >40% i.e., can DUO-EF predict future development of LVEF <40%
 - DUO-EF point-of-care determination of LVEF<40% in comparison with the components of the established NICE pathway (BNP result)

POPULATION

- **Group 1:** All-comers to **echocardiography** and cardiac MRI departments across Imperial College Healthcare NHS Trust (**echo n = 1,500**, cMRI n = 100)
- **Group 2:** Patients seen in primary care (GP) with symptoms newly suggestive of heart failure (n = 400); contributing to Group 1 if standard of care indicates need for referral to echo/cMRI
- **Group 3:** Patients seen in the COVID-19 follow-up clinic with symptoms newly suggestive of heart failure (n = 400); contributing to Group 1 if standard of care indicates need for referral to echo/cMRI

ELIGIBILITY

Inclusion criteria for all	
 - Age 18 years or above - Able to give informed consent 		
	Group 1	Group 2	Group 3
Additional inclusion criteria	
 - Patient attending for departmental echo or cardiac MRI 	
 - Attending for GP appointment; GP concerned about heart failure diagnosis and initiates patient onto routine NICE pathway 	
 - Attending COVID-19 follow-up clinic; clinician concerned about heart failure diagnosis and initiates patient onto routine NICE pathway

Exclusion criteria	Any chest wound, skin pathology or other feature that would prohibit routine stethoscope examination
---------------------------	--

DURATION Start date 01/02/2021, duration 36 months

[figure not shown]
STUDY WORKFLOW SUMMARY DIAGRAM ON NEXT PAGE

DUO-EF-19: Diagnosis of Heart Failure in the Post-COVID-19 Clinic, Primary Care and Hospital Setting Using a Digital Stethoscope with AI ECG

Study Workflow

[figure not shown]
Imperial NHS Trust Echocardiography and Cardiac MRI Departments

St Mary's, Hammersmith & Charing Cross Hospitals and Community Cardiology Centres

[figure not shown]
GP Practices

NIHR North West London Clinical Research Network portfolio support

COVID-19 Clinic

All-comers to COVID-19 follow up clinic at St Mary's Hospital

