1. INTRODUCTION

1.1 BACKGROUND

Heart Failure

One million people in the UK are living with heart failure (HF), with more than 60,000 new cases annually. Consuming 2% of the entire NHS budget, HF has a worse prognosis — 50% mortality within five years — than most cancers. Furthermore, hospital admissions and demand for social care related to HF is expected to increase by 50% by 2040.¹ Given this massively increasing prevalence of HF, the evidence for the benefits of early diagnosis and treatment coupled with the importance of accuracy and difficulty in diagnosis, HF is one of the biggest challenges facing the NHS, for which better, early diagnostic and management strategies are urgently needed.

HF is a clinical syndrome with a wide spectrum. The majority of patients with HF have heart failure with reduced ejection fraction (HFrEF), characterised by a reduction in blood pumped out of the left ventricle with each heartbeat, as seen on an echocardiogram (an ultrasound-based medical imaging tool, where above 50% is considered normal ejection fraction). **HFrEF is defined as a left ventricular ejection fraction (LVEF) below 40%.** The clinical syndrome of heart failure with preserved ejection fraction (HFpEF) features similar clinical symptoms (e.g. breathlessness, fatigue, ankle swelling) to HFrEF. However, it is difficult to diagnose and no treatment has been proven in pivotal clinical trials to be effective for HFpEF,² the mortality from which is lower than treated HFrEF, even when optimally managed.

There is strong and abundant evidence that early effective drug therapy can improve symptoms and prognosis in patients with HFrEF (LVEF <40%), where a substantial portion of increased morbidity and mortality is attributable to late initiation of therapies — caused by delayed diagnosis.³

HF is poorly served in primary care, as it can be difficult to diagnose from non-specific symptoms. Delays in diagnosis lead to late initiation of life-prolonging therapies. Current clinical management guidelines from the National Institute for Health and Care Excellence (NICE) suggest performing a brain natriuretic peptide blood test (BNP) when HF is suspected. According to the NICE guidelines, if BNP is elevated, the GP makes a referral for specialist tests (echocardiogram) and assessments within six weeks - two weeks if BNP is especially high.¹

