All study participants will be approached to take part and have a DUO-EF reading during the course of their routine care (minimal disruption) in the echo or cardiac MRI setting, during their GP appointment, or while attending COVID-19 follow up clinic. This will result in a large, representative study population to meet the objectives of testing the hypothesis for DUO-EF as a screening tool.

Group 1: Departmental Echocardiography and Cardiac MRI, Imperial College Healthcare NHS Trust

Unselected patients attending for departmental echocardiography (n = 1,500) and subgroup in cardiac MRI (n = 100). Patients will be consented by a member of the research team while they wait for an echocardiogram/cMRI. Patients from group 2 (GP referrals) will also be attending for an echo as part of their routine care on the heart failure pathway; they will be re-consented by a member of the research team upon arrival in the department.

Researchers will perform and record DUO-EF readings on participants and subsequently review echocardiography and cardiac MRI reports and document the LVEF calculated by these modalities.

If echocardiography does not suggest heart failure with LVEF<40% but DUO-EF does, patients will be followed-up with a **24 month phone call** (early evidence indicates the algorithm can identify low ejection fraction before being detectable on echo⁸).

Group 2: Patients in Primary care ('real world' evaluation)

NIHR North West London Primary Care **Clinical Research Network** (n = 10 GP practices). Patients attending GP with signs/symptoms of heart failure (n = 400 in total across all sites) will proceed with standard-of-care NICE heart failure pathway, with no change to standard of care through participation in study. GP's will be asked to record DUO-EF in any patient where heart failure is suspected.

Researchers will capture the point-of-care DUO-EF prediction from the GP:

- Comparing this to repeat DUO-EF ('agreement' between two time points) at time of (group 1) echocardiography (if indicated by standard of care investigations: BNP and 12-lead ECG)
- And comparing both of these DUO-EF measurements to echocardiography derived LVEF

Group 3: COVID-19 Clinic, Imperial College Healthcare NHS Trust

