An interim analysis will be conducted (anticipated at 3 months) when the study has recruited n = 400 patients with paired DUO-EF and echocardiography results. Based on the previous power calculation this should be sufficient to indicate with 90% power if we can reject a null hypothesis that the AUC <0.7 at the 0.05 level of significance.

Missing Data

The study design and nature of the variables collected makes missing data unlikely. In order to avoid introducing bias into the dataset by removal of participants with any missing data, all participants will be retained; missing of any variable will entail the affected participant not being included only in the analyses specifically relevant to that variable. Access to shared primary and secondary care electronic health records should make missing data retrievable in most cases. Details of any missing data will be explicitly described in any reports or publications.

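### DUO-EF positives in Group 2 (and possibly Group 3) who are not referred for echo or cMRI are neither verified nor followed, so a PPV for these settings is probably biased upward by an amount the protocol cannot fix

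*Protocol*

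**What the plan says.** Aim 3 in the Study Summary is "To evaluate the positive and negative-predictive value of DUO-EF at 24 months". The reference is set in Aim 1, where DUO-EF is "compared to gold-standard investigations for calculating LVEF (echocardiography [echo], and a subgroup in cardiac MRI [cMRI"). BNP is a comparator and not a gold standard.

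For Groups 2 and 3 the Study Summary (Population) describes patients as "contributing to Group 1 if standard of care indicates need for referral to echo/cMRI". Section 3, Group 2, says what decides this: the repeat DUO-EF at echo takes place "if indicated by standard of care investigations: BNP and 12-lead ECG". Section 1.1 gives the routine rule: "if BNP is elevated, the GP makes a referral for specialist tests (echocardiogram"). A positive DUO-EF does not itself lead to imaging, since section 5 says that "DUO-EF is not interfering with the standard of care".

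The only planned later contact is in section 6: "Follow-up phone call at 24 months for all patients with positive DUO-EF but negative gold standard investigations for LVEF <40"%. Section 3 (Group 1) and Appendix 1 use the same trigger. On missing data, section 7 says that "missing of any variable will entail the affected participant not being included only in the analyses specifically relevant to that variable".

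**The concern.** Read together, these provisions leave one kind of patient unobserved: positive on DUO-EF at the point of care, and not referred because BNP and ECG did not indicate it. Without an echo or cMRI this patient is not gold-standard negative, so no call is made. With no LVEF on record, the missing-data rule leaves the patient out of the comparison as well.

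PPV is a proportion of all test positives. If only the positives that BNP and ECG also selected are verified, the result is the PPV of DUO-EF combined with the existing pathway. Group 2 is described as the real-world evaluation of a screening tool, so this would answer a different question from the one asked. The usual name for the problem is partial verification bias. It has to be settled in the protocol, because outcomes that were never collected cannot be recovered by any later analysis.

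**Working it through.** **The plan's own figures.** The protocol gives no PPV, no referral rate and no prevalence for Groups 2 and 3. Its one derived sample size, 466 per LVEF class, reproduces: an exact binomial test of 0.80 against 0.85 with upper tail 0.025 first reaches 80% power at n = 466 (critical count 390, power 0.805). This point does not touch that figure.

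**Inputs from the protocol.** Group 2 n = 400; Group 3 n = 400; Group 1 echo n = 1,500 with about half below 40% LVEF; sensitivity and specificity 85% (sample-size alternative) or 80% (manufacturer).

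**Assumptions.** Share referred R = 30, 50 or 70%; prevalence of low LVEF in the referred p_r = 10, 20 or 30%; in the unreferred p_u = 0, 1 or 3%.

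**Formulas**, with Se = Sp:
- Referred: TP_r = 400·R·p_r·Se and FP_r = 400·R·(1−p_r)·(1−Sp).
- Unreferred: TP_u = 400·(1−R)·p_u·Se and FP_u = 400·(1−R)·(1−p_u)·(1−Sp).
- PPV as observed = TP_r/(TP_r+FP_r).
- PPV over all positives = (TP_r+TP_u)/(TP_r+FP_r+TP_u+FP_u).

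**Central case** (Se = Sp = 85%, R = 50%, p_r = 20%, p_u = 1%):
- TP_r = 200 × 0.20 × 0.85 = 34; FP_r = 200 × 0.80 × 0.15 = 24.
- TP_u = 200 × 0.01 × 0.85 = 1.7; FP_u = 200 × 0.99 × 0.15 = 29.7.
- Observed PPV = 34/58 = 58.6%. PPV over all positives = 35.7/89.4 = 39.9%. The difference is 18.7 points.
- Unverified positives: 1.7 + 29.7 = 31.4.
- Bounds without knowledge of LVEF in the unverified: all false, 34/89.4 = 38.0%; all true, (34 + 31.4)/89.4 = 73.2%.

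**Whole grid.**

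| Se = Sp | Overstatement (points) | Positives not observed per 400 |
|---|---|---|
| 85% | 5.9 to 34.9 | 18 to 48 |
| 80% | 5.2 to 34.8 | 24 to 61 |

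The share of Group 2 false positives that goes unseen is 32% to 77% over the grid; at R = 70% it is 32% to 38%.

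**Dependence on the referral mechanism.** The grid always gives the referred a higher prevalence, so it cannot return zero. A second parametrisation can. Take Groups 2 and 3 together (n = 800), Se = Sp = 80% and prevalence 20%. Then TP = 160 × 0.80 = 128, FP = 640 × 0.20 = 128, and the PPV over all positives is 0.50. Let r1 and r0 be the referral probabilities with low and with higher LVEF. The observed PPV is 128·r1/(128·r1 + 128·r0):
- r1 = r0 = 0.5: 0.50, no bias.
- r1 = 0.95, r0 = 0.8: 121.6/224 = 0.54.
- r1 = 0.95, r0 = 0.5: 121.6/185.6 = 0.66.
- r1 = 0.95, r0 = 0.3: 121.6/160 = 0.76.

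**Pooling with Group 1** (central Group 2 case, Se = Sp = 85%, Group 2 counted in addition to the 1,500). Group 1 gives TP = 750 × 0.85 = 637.5 and FP = 750 × 0.15 = 112.5. Observed PPV is (637.5 + 34)/(750 + 58) = 671.5/808 = 83.1%. Over all positives it is (637.5 + 35.7)/(750 + 89.4) = 673.2/839.4 = 80.2%. The shift is about 3 points.

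**The case against.** Several stronger readings suggest themselves, and the protocol does not support them.

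- A reader might infer that most false positives in these groups are lost. That needs fewer than half of them to be referred. No referral rate is given, and at 70% referral the lost share is about a third.
- A reader might take the overstatement as established. It is an inference: within a group, PPV is unbiased if referral is unrelated to LVEF among DUO-EF positives. The direction is still likely, because section 1.1 has elevated BNP lead to echo when heart failure is suspected.
- Aim 3 names no setting. If PPV is pooled over all groups, the effect is small. The large figures apply only to a PPV for the primary-care or COVID-19 clinic setting.
- A reader might assume the gap is the same in Group 3. The Study Summary (Population) makes its echo conditional, but Methods item 3 and the Group 3 text in section 3 carry no such condition. If every Group 3 patient has an echo, the gap is confined to Group 2.
- A reader might see the unreferred positives as the cases the future-risk objective is looking for. Section 2 defines that objective in patients whose gold standard showed LVEF above 40%. Without a baseline LVEF, low LVEF at 24 months cannot be called new.
- PPV appears in Aim 3 but not in the objectives or outcome measures, and its exact denominator may properly be left to an analysis plan. Section 7 also expects most missing data to be retrievable from shared records and promises to describe what is missing.

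These arguments limit the size and scope of the point, but the gap remains. An echo that was never done cannot be retrieved, and who is followed up is fixed by the protocol. Separately, no call is planned for DUO-EF negatives, so the calls cannot supply the 24-month NPV in Aim 3 either. That is a further problem with the aim and does not answer this one.

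**Conclusion.** The point holds in limited form. Unreferred DUO-EF positives in Group 2, and in Group 3 if its echo is conditional, fall outside both the gold-standard comparison and the 24-month call. A PPV for these settings is therefore exposed to verification bias, probably upward. The size cannot be determined from the protocol: illustratively 0 to about 35 points within Group 2, 19 points in the central case, and about 3 points in that case when pooled with Group 1. These values rest on assumed referral rates and prevalences and on accuracy of 80% or 85%. Because a participant counts as positive if any one of five readings is positive, specificity could be lower than assumed and the number of unverified positives higher. This concerns a secondary aim, and the gap is cheap to narrow before follow-up begins.

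**What to change.** 1. Extend the 24-month trigger in section 3 (Study Participant Population), section 6 and Appendix 1 to participants with a positive DUO-EF whose gold standard was not performed. Align the matching sentences in the Study Summary and section 3.1. Use the existing call and a shared-record check for any later LVEF or heart failure diagnosis. Referral and care do not change.
2. Report these participants as a separate row, with the referral rate among DUO-EF positives in each group.
3. State the PPV denominator. Give PPV among verified positives together with bounds (all unverified positives false; all true) or a verification-bias correction. Do not count unverified positives as false by default: neither a call nor a record check measures LVEF, so that would bias PPV downward.
4. Keep the objective on new LVEF below 40% restricted to participants with a baseline gold standard above 40%.
5. Reconcile the Study Summary (Population) with Methods item 3 and the Group 3 text in section 3 on whether Group 3 echo is conditional.

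The cost is a short amendment, roughly 20 to 60 extra calls or record checks per 400 patients under the assumptions above, and a wider, less favourable PPV statement.

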2. STUDY OBJECTIVES

Primary objective:

1. **To test if the DUO-EF algorithm can achieve a sensitivity and specificity above 80% for detection of LVEF above or below 40% in comparison to gold-standard echocardiography**

Secondary Objectives:

- To perform a subgroup analysis of DUO-EF against LVEF calculated by cardiac MRI (another gold standard investigation for calculating LVEF <40%)
- To validate consistency of DUO-EF result at point-of-care in GP practice ('real world' use where GP suspects new heart failure) against repeat DUO-EF at time of gold-standard investigation
- To validate consistency of DUO-EF result at point-of-care in Covid-19 follow up clinic ('real world' use where clinicians suspect new heart failure) against repeat DUO-EF at time of gold-standard investigation
- To measure if participants with DUO-EF suggestive of LVEF <40% but with gold standard investigations where LVEF >40% are at increased risk of developing heart failure at 24 months i.e. can DUO-EF predict future development of LVEF <40% at 24 months
- To evaluate DUO-EF point-of-care determination of LVEF<40% in comparison with the components of the established NICE primary care pathway (e.g. BNP result)

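### Deaths found before the 24-month call have no role in the future-risk outcome and can drop out of its denominator, biasing the proportion in either direction

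*Protocol*

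**What the plan says.** The secondary outcome in Protocol section 3.1 is "Development of LVEF <40% at 24 months in participants with initial DUO-EF suggestive of LVEF <40% but gold standard investigations LVEF >40" per cent. The matching objective in section 2 asks whether these participants "are at increased risk of developing heart failure at 24 months". The only scheduled follow-up is the phone call in section 6, and before it is made "we will first attempt to confirm whether or not the participant is deceased by review of the NHS Spine, thereby avoiding unnecessary distress for relatives". No other purpose is given for that check.

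Death appears nowhere in the outcome. The list of data captured from the electronic health record (EHR) in section 7 includes echo and cardiac MRI LVEF, but not vital status, date of death or cause of death. Section 5.3.2 exempts death from SAE reporting.

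The Missing Data paragraph of section 7 retains all participants, but "missing of any variable will entail the affected participant not being included only in the analyses specifically relevant to that variable". It then adds: "Access to shared primary and secondary care electronic health records should make missing data retrievable in most cases". It also promises to describe missing data in reports. It does not mention death.

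**The concern.** For an outcome of progression to low LVEF or heart failure, death is not an ordinary missing value. It ends the chance of observing progression, and it may be related to progression: the protocol itself gives heart failure "50% mortality within five years". A plan that looks up vital status but gives it no place in the analysis leaves only the general missing-data rule. Under that rule, whether a deceased participant stays in the denominator depends on whether a later LVEF happens to be on record.

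At stake is the 24-month proportion that is meant to answer "can DUO-EF predict future development of LVEF <40" per cent. If the denominator is selected in part by the outcome, the result is neither the risk among everyone due a call nor cleanly the risk among survivors.

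**Working it through.** The protocol states no event rate, death rate or precision for the 24-month outcome, so there is no figure of its own to reproduce. Its sample size serves the primary objective only.

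**Step 1. The sections side by side**
- Section 6: death is ascertained, and the stated purpose is to spare relatives.
- Section 3.1: death is neither an event nor a competing event.
- Section 7, data list: date and cause are not captured.
- Section 7, Missing Data: a participant who lacks the variable leaves that analysis, unless the records supply it.

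The deceased therefore split into those with a retrievable later LVEF, who can be counted, and those without, who are excluded.

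**Step 2. How many are due a call**

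Number = (participants with LVEF above 40%) × (1 − specificity). Section 3 gives a minimum of 500 with LVEF above 40%. Half of the planned 1,500 echo participants is 750. Specificity is 80% (manufacturer) or 85% (the alternative in the power calculation).
- 500 × 0.15 = 75
- 500 × 0.20 = 100
- 750 × 0.15 = 112.5
- 750 × 0.20 = 150

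That is about 75 to 150 people.

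**Step 3. How many might die**

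No mortality figure is given for this group. The section 1.1 figure for people with heart failure implies 1 − 0.5^(2/5) = 24.2% dead at two years under a constant hazard. That is an upper-end assumption here, because this group had a gold-standard LVEF above 40%. Deaths of 5%, 10% or 24% among 75 to 150 people are about 4 to 8, 8 to 15, or 18 to 36.

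**Step 4. Effect of the rule**

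Let n be due a call, with D deaths and S = n − D survivors. Let r be the survivors' event rate, q the share of the deceased who reached LVEF <40% before death, and c the share of those events that is documented and retrieved. Assume complete status in survivors, and no retrievable later LVEF in the other deceased.
- True risk = (S·r + D·q) / n
- Risk under the available-case rule = (S·r + c·D·q) / (S + c·D·q)

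All rates below are assumptions. The percentages depend on the rates, not on n.

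| Case | True risk | Rule, c = 0 | Rule, c = 0.75 | Rule, c = 1 |
|---|---|---|---|---|
| A: n 200, D 30, r 10%, q 40% | 29/200 = 14.5% | 17/170 = 10.0% | 26/179 = 14.5% | 29/182 = 15.9% |
| B: n 200, D 10, r 10%, q 40% | 23/200 = 11.5% | 19/190 = 10.0% | 22/193 = 11.4% | 23/194 = 11.9% |
| C: n 100, D 10, r 5%, q 30% | 7.5/100 = 7.5% | 4.5/90 = 5.0% | 6.75/92.25 = 7.3% | 7.5/93 = 8.1% |

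The sign of the error depends on c, which the protocol does not settle. If the deceased progressed at the survivors' rate and none of it was documented, there is no error: in case A with q = 10%, (17 + 3)/200 = 10.0% = 17/170.

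**Step 5. What full-denominator reporting gives**

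Keep all n in the denominator. Counting only documented events gives (S·r + c·D·q)/n. Counting LVEF <40% or any death gives (S·r + D)/n.

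| Case | Documented events, c = 0 | Documented events, c = 1 | Composite with death |
|---|---|---|---|
| A | 17/200 = 8.5% | 29/200 = 14.5% | 47/200 = 23.5% |
| B | 19/200 = 9.5% | 23/200 = 11.5% | 29/200 = 14.5% |
| C | 4.5/100 = 4.5% | 7.5/100 = 7.5% | 14.5/100 = 14.5% |

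With c = 0 in case A, the documented-event figure of 8.5% is further from the truth than the 10.0% under the rule. It is therefore not enough alone. Together with the composite it brackets the true risk in every case.

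**The case against.** The strongest reply is that section 7 already points to the remedy. It expects records to make most missing data retrievable, and LVEF from echo and MRI is on the capture list, so a low LVEF measured before death is a value the study expects to find. The rule does not name death, and a statistical analysis plan, not shown here, could define how deaths count. Section 3 notes that many people referred for echo turn out to have no abnormality, so deaths may be few. The outcome is secondary.

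Much of this stands, and it rules out several stronger readings that a reader might infer:
- **All the deceased are dropped, so the rate is for survivors only.** Not supported: the records sentence allows some to be counted.
- **The bias is towards zero.** Not supported: step 4 shows either sign.
- **The worst heart-failure courses are removed.** Conjecture: deaths may be from any cause, and severe disease is more likely to have been imaged.
- **About 24% of this group will die.** Not supported: the figure is for people with heart failure.
- **The error works against a comparison.** Not supported: section 6 follows only DUO-EF-positive, gold-standard-negative participants, so the result is a single proportion with no contrast to dilute.

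What does not stand is that nothing needs changing. The records sentence is a general expectation. It requires no search after a confirmed death and leaves open what happens when no later LVEF exists. The available-case rule is already fixed in the protocol, and capturing date and cause of death is a data-collection matter, not only an analysis choice.

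**Conclusion.** The point holds in limited form. Read literally, the protocol treats death before 24 months as ignorable missing data for the future-risk outcome, and deceased participants with no retrievable later LVEF leave the denominator. The resulting proportion can be too low or too high.

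In the illustrations the error runs from 4.5 percentage points too low to 1.4 too high (case A, 10.0% and 15.9% against 14.5%) and shrinks with fewer deaths. These sizes rest on assumed death, progression and documentation rates, and the protocol supplies none of them for this group. One secondary outcome is affected. The single-visit sensitivity and specificity of the primary outcome are not. It should be corrected, but it does not threaten the main result.

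**What to change.** - **Sections 6 and 7 (data list):** when the Spine shows a death, record its date and, where available, its cause. Search the shared EHR for any LVEF or heart failure diagnosis after baseline.
- **Section 7, Missing Data:** exempt deaths from the available-case rule. Keep all participants due a call in the denominator, count a documented LVEF <40% before death as an event, and report other deaths separately as a competing event.
- **Supporting analysis:** add a composite of LVEF <40% or death from any cause, and one with heart-failure death where the cause is known. Read with the documented-event proportion, the all-cause composite bounds the effect of undocumented progression.

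The cost is some wording and a small record look-up for people whose Spine entry is already being checked. Cause of death will be incomplete for some, which is why the all-cause composite is needed.
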